4.5.2. Adverse Events of Special Interest (applicable to cemiplimab only)

All AEs of special interest (AESI), serious and nonserious, must be reported to the Sponsor within 24 hours of identification. AEs of special interest for this study include:

- Grade ≥ 2 infusion-related reaction (IRR)
- Grade ≥ 2 allergic/hypersensitivity reactions
- Grade ≥ 3 immune-mediated adverse event (imAE)
- An imAE of any grade in a patient previously treated with a PI3-Kinase inhibitor

Note: An imAE can occur shortly after the first dose, several months after the last dose of treatment, or any time in-between. All AEs of unknown etiology associated with drug exposure should be evaluated to determine possible immune etiology. If an imAE is suspected, efforts should be made to rule out neoplastic, infectious, metabolic, toxin or other etiologic causes prior to labeling an AE as an imAE.

4.5.3. Laboratory Safety Variables

The clinical laboratory data consists of serum chemistry, hematology, urinalysis and other.

Clinical laboratory values will be converted to standard international (SI) units and grouped by function in summary tables. Conventional units may be provided. Functions are defined as follows:

Blood Chemistry: Sodium; Potassium; Chloride; Calcium; Glucose; Albumin; Total protein, serum; Creatinine; Aspartate aminotransferase (AST); Alanine aminotransferase (ALT); Alkaline phosphatase; Carbon dioxide (bicarbonate); Blood urea nitrogen (BUN); Bilirubin (total/direct); Uric acid

Hematology: Hemoglobin; White blood cells (WBCs); Platelet count; Differential (Neutrophils, Lymphocytes, Monocytes)

Urinalysis: pH; Ketones; Glucose; Specific gravity; Protein; Blood

Other Laboratory Tests: Thyroid Function Tests; Coagulation Tests; Viral Serology Tests; Pregnancy Tests

4.5.4. Vital Signs

Vital signs will be collected according to the protocol: Body temperature (°C); Resting systolic blood pressure and diastolic blood pressure (mmHg); Pulse (beats/minute); Respiratory rate (breaths/minute)

4.5.5. 12-Lead Electrocardiography (ECG)

A standard 12-lead ECG will be performed at time points according to the protocol. 12-Lead ECG parameters include PR, QRS, RR, and QT (identify QTcB or QTcF) intervals; Heart Rate (recorded from the ventricular rate)

Any ECG finding that is judged by the investigator as a clinically significant change (worsening) compared to the baseline value will be considered an AE, recorded, and monitored. If a clinically significant finding is identified and assessed as not related to study drugs by the investigator, an alternative aetiology for the abnormality should be provided in the AE page.

4.5.6. Physical Examination Variables

A complete or limited physical examination will be performed at visits specified in the protocol. Care should be taken to examine and assess any abnormalities that may be present, as indicated by the patient's medical history.

Complete physical examination will include examination of head and neck, lungs, heart, abdomen (including liver and spleen), lymph nodes, extremities, and skin, as well as a brief neurologic examination.

Limited physical examination will include examination of lungs, heart, abdomen, skin, and other organ systems.

Any finding that is judged by the investigator as a clinically significant change (worsening) compared to the baseline value will be considered an AE, recorded, and monitored. If a clinically significant finding is identified and assessed as not related to study drugs by the investigator, an alternative aetiology for the abnormality should be provided in the AE page.

4.6. Pharmacokinetic Variables and Anti-Drug Antibody Variables (ADA)

4.6.1. Pharmacokinetic Variables

Serum samples for cemiplimab will be collected from all patients as follows:

- Pre-dose (C_{trough}) on cycle 1 day 1 and every other cycle for the first 2 years of treatment
- Pre-dose (C_{trough}) every 6 months (24 weeks) thereafter during therapy and at EOT.

4.6.2. Immunogenicity Variables

The immunogenicity variables are ADA status, titer, and time-point/visit. Serum samples for ADA will be collected at the clinic visits specified in the table 1 of the protocol.

5. STATISTICAL METHODS

For continuous variables, descriptive statistics will include the following: the number of patients reflected in the calculation (n), mean, median, standard deviation, minimum, and maximum. In addition, 25th percentile and 75th percentile will be provided.

For categorical or ordinal data, frequencies and percentages will be displayed for each category. The denominator will be determined by the analysis population used for the summary.

For time-to-event variables, median time-to-event (and the survival rate at a fixed time point) and its two-sided 95% confidence intervals will be summarized by the Kaplan-Meier method, unless otherwise specified.

5.1. Demographics and Baseline Characteristics

Patient demographics and baseline characteristics variables listed in Section 4.1 will be summarized descriptively.

5.2. Medical History

Medical history will be summarized by SOC and PT. Tables will be sorted by decreasing frequency of SOC followed by PT.

5.3. Prior/concomitant Medications and Procedures

Prior medications and procedures will be summarized.

The number and percentage of patients who received any prior cancer related medications, prior cancer related radiotherapy, or prior cancer related surgery will be summarized.

Concomitant medications will be summarized by ATC level 2 and ATC level 4. Concomitant procedures will be summarized by SOC and PT.

5.4. Subject Disposition

For subject disposition, the following summaries will be provided:

- The total number of screened patients
- The total number of patients in each analysis set
- The total number of patients who discontinued the study treatment and the reasons for the treatment discontinuation
- The total number of patients who discontinued the study, and the reasons for the study discontinuation

5.5. Protocol Deviation

Protocol deviations will be defined in separate protocol deviation plan (PDP). Listing of all patients with protocol deviations and the reason of deviation will be provided. The important protocol deviation, such as violation of inclusion/exclusion criteria; post-enrollment deviations

which will impact assessment of efficacy or safety endpoints, will be determined before database lock and be summarized.

5.6. Extent of Study Treatment Exposure and Compliance

5.6.1. Measurement of Compliance

Drug compliance records, including actual drug administration will be provided.

5.6.2. Exposure to Investigational Product

Exposure to ISA 101b and cemiplimab will be examined for each subject and the following variables will be calculated:

- The total number of study doses administered
- The total dosage of study drug administered
- Duration of treatment exposure (in weeks) calculated as the minimum of
 - $[\text{date of last dose} - \text{date of first dose} + 21 \text{ days}] / 7$
 - or
 - $[\text{date of clinical data cut-off or date of death} - \text{date of first dose} + 1] / 7$
- The number and percentage of subjects exposed to cemiplimab will be presented by specific time point of interest.
- The actual dose intensity ($\mu\text{g} / \text{week}$) = total dose received (μg) / duration of treatment exposure (week) for ISA 101b
The actual dose intensity (mg / week) = total dose received (mg) / duration of treatment exposure (week) for cemiplimab
- The relative dose intensity = actual dose intensity / planned dose intensity
 - Planned dose intensity ($\mu\text{g} / \text{week}$) = planned dose (μg) / 3 for ISA 101b
 - Planned dose intensity (mg / week) = planned dose (mg) / 3 for cemiplimab

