8.2. Dose Modification and Study Treatment Discontinuation Rules

8.2.1. Dose Modification

Dose modification of cemiplimab for an individual patient is not allowed.

If cemiplimab is delayed, interrupted, or discontinued due to toxicity clearly related to cemiplimab as described in the cemiplimab Investigator's Brochure, and this toxicity is not considered related to ISA101b, the remaining doses of ISA101b may be administered. It is recommended to discuss such cases with the Medical Monitor.

If ISA101b is delayed, interrupted, or discontinued due to toxicity clearly related to ISA101b as described in the ISA101b Investigator's Brochure, and this toxicity is not considered related to cemiplimab, the remaining doses of cemiplimab may be administered. It is recommended to discuss such cases with the Medical Monitor.

There will be no dose reduction for ISA101b in this study.

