11.4.5.3. Treatment Exposure

Duration of exposure, number of doses administered, and dose intensity will be summarized.

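### Cemiplimab dose intensity in SAP 5.6.2 counts the last dose in full but cuts its 21-day interval at death or data cut-off, so some on-schedule patients score above 100%

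*SAP*

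**What the plan says.** Protocol 11.4.5.3 sets the requirement: "Duration of exposure, number of doses administered, and dose intensity will be summarized". SAP 5.6.2 supplies the definitions, applied to ISA101b and cemiplimab separately.

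- Duration: "Duration of treatment exposure (in weeks) calculated as the minimum of" two terms, each divided by 7. The first is last dose minus first dose plus 21 days. The second is data cut-off or death minus first dose plus 1 day.
- Actual intensity: "The actual dose intensity (mg / week) = total dose received (mg) / duration of treatment exposure (week) for cemiplimab".
- Planned intensity: "Planned dose intensity (mg / week) = planned dose (mg) / 3 for cemiplimab".
- Ratio: "The relative dose intensity = actual dose intensity / planned dose intensity".

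Neither document prorates the last dose when the second duration term applies, and neither limits the ratio to 100%. On the dose itself, Protocol 8.2.1 states: "Dose modification of cemiplimab for an individual patient is not allowed".

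**The concern.** Truncating at death or cut-off is sensible for describing how long a patient was exposed. It does not suit a dose-intensity denominator. Planned intensity assigns each 350 mg dose a 21-day interval. When the second duration term is the smaller, the last dose stays whole in the numerator while its interval is shortened in the denominator, so the ratio rises although no extra drug was given.

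The dose is fixed, and Protocol 9.1 says missed cemiplimab doses are not made up. Values well above 100% would therefore come from the formula and not from over-delivery. The error has one direction, so it can also cancel part of the drop that a missed dose should cause. SAP 5.6.1 reduces compliance to administration records, which leaves relative dose intensity as the only calculated ratio of delivered to planned drug in SAP 5.6.

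**Working it through.** The SAP states no dose-intensity value, so there is no figure to reproduce. The formulas were applied directly.

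**Inputs**
- Dose 350 mg; cemiplimab on study days 8, 29, 50, 71 and so on (SAP 2.3). With cycles of 7, 6 and 9 weeks, every gap is 21 days.
- Planned intensity: 350/3 = 116.67 mg per week.
- The first dose is read as the first cemiplimab dose, because exposure is calculated per drug.
- k = number of on-schedule doses; d = days from last dose to death or cut-off.

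**Formula**

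The first term is 21(k−1) + 21 = 21k days. The second is 21(k−1) + d + 1 days. Dividing actual by planned intensity, the 350 mg cancels:

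RDI = 21k / min(21k, 21(k−1) + d + 1)

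For d ≥ 20 the result is exactly 100% for every k. Planned intensity therefore matches the schedule, and the truncation alone produces any excess. For d from 0 to 19 the result exceeds 100%.

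**Patients still on treatment at cut-off**

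On schedule, d runs from 0 to 20, so 20 of the 21 possible values are affected. The primary cut-off waits for the last patient's opportunity for four tumor assessments (SAP 5.7.1). The fourth is cycle 4 day 43, which is study day 49 + 42 + 42 + 43 = 176. That is also the scheduled ninth dose: 8 + 8 × 21 = 176.
- k = 9, d = 0: 189/169 = 111.8%
- k = 9, d = 10: 189/179 = 105.6%
- k = 16, d = 10: 336/326 = 103.1%

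**Early deaths**
- k = 3, d = 10: 63/53 = 118.9%
- k = 2, d = 7: 42/29 = 144.8%
- k = 2, d = 0: 42/22 = 190.9%, the maximum from two doses on
- k = 1, d = 9: 21/10 = 210%; k = 1, d = 10: 21/11 = 190.9%

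So 200% or more needs a single dose and d ≤ 9.

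**Masking of missed doses**
- Eight of nine scheduled doses given, dosed on the cut-off day: 168/169 = 99.4%. Without truncation: 168/189 = 88.9%.
- Dosed on days 8 and 50, day 29 missed, death 7 days after the last dose: 42/50 = 84.0%. Without truncation: 42/63 = 66.7%.

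**If first dose meant study day 1**

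Both terms gain 7 days. On-schedule RDI then exceeds 100% for d ≤ 12, and untruncated on-schedule patients fall below 100% (k = 1: 21/28 = 75%; k = 8: 168/175 = 96%). The mismatch remains under either reading.

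**The case against.** The strongest reply is that this matters little.

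- **Extremes are rare.** A reader might infer that values of several hundred percent will be common. The documents do not support that. Values of 200% or more need one dose and death or cut-off within 9 days. Eligibility requires ECOG 0 or 1 and an anticipated life expectancy of at least 20 weeks (Protocol 7.2.1). At the primary cut-off the last patient is about 168 days past the scheduled first cemiplimab dose, so essentially only deaths could produce such values there. This stands.
- **No shift in the mean can be stated.** A reader might want one, but the documents give neither the number nor the timing of early deaths. Suppose 5 of 105 patients die early, two after one dose and three after two. With d uniform on 0 to 19, average RDI is about 378% and 138%, and the mean rises by (2 × 278 + 3 × 38)/105 = 6.4 points. With d uniform on 3 to 19 the rise is 3.1 points, and on 7 to 19 it is 1.8. The assumption drives the answer. The share of patients truncated at cut-off likewise depends on a time to progression that the documents do not give.
- **Robust summaries are planned.** SAP 5 also calls for median, quartiles, minimum and maximum. If fewer than a quarter of patients are truncated and the rest are on schedule, the median and both quartiles stay at 100%, and the maximum would expose an odd value. This limits the harm but does not make the formula right.
- **Visit windows also move the ratio.** A first dose 3 days late and a last dose 3 days early give 42/36 = 117% at two doses and 189/183 = 103% at nine, with no truncation. This is true, but windows act in both directions; truncation only raises the ratio.
- **Other measures are intact.** Number of doses and total dosage, also in SAP 5.6.2, are untouched. Protocol 11.4.5.3 names dose intensity but not relative dose intensity, so calling the ratio the trial's test of deliverability would go beyond the text.

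None of this removes the mismatch between numerator and denominator.

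**Conclusion.** The formula is wrong as written for cemiplimab dose intensity, and the consequence is minor. On-schedule patients whose death or cut-off falls 0 to 19 days after the last dose score above 100%. For those still on treatment at the primary cut-off the excess is at most about 12 percentage points and shrinks with further doses. Early deaths after two or more doses can reach 191%; anything from 200% up is a rare single-dose case. The bias is always upward and can hide a missed dose almost completely.

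These figures assume perfectly timed doses and that first dose means first cemiplimab dose. A reader might infer that efficacy conclusions are affected. They are not: ORR, DOR, PFS and OS do not use this duration, and no decision rule depends on dose intensity.

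**What to change.** In SAP 5.6.2, keep the minimum rule for the duration-of-exposure summary only. For cemiplimab actual and relative dose intensity, use (last dose − first cemiplimab dose + 21 days)/7 as the denominator, with no truncation at death or data cut-off. Perfectly on-schedule patients then score 100%, and a dose missed between the first and last doses received shows in full.

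The cost is one sentence and a small programming change. SAP 1 allows revision before database lock. Reported relative dose intensity will be slightly lower. Two limits remain: visit windows can still move the ratio slightly off 100%, and doses missed after the last one received are still not reflected. The ratio should therefore be read beside the number of doses administered.

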6. STUDY DESIGN

6.1. Study Description and Duration

This will be a single-arm, phase 2, global study of treatment with cemiplimab + ISA101b in HPV16-positive cervical cancer patients with disease progression on first line chemotherapy in the recurrent or metastatic setting. Study treatment and duration include cemiplimab every 3 weeks (with 3 doses of ISA101b on days 1, 29, and 50) until progression or any reason for early discontinuation as outlined in Section 7.3 and Section 8.2.2.

Patients will undergo screening evaluations to determine eligibility within 28 days prior to first treatment. All patients will receive the following regimen:

- ISA101b 100 µg/peptide by SC injection on day 1, day 29, and day 50 (total of 3 doses).
- Cemiplimab 350 mg given by IV infusion over 30 minutes Q3W on days 8 and 29 in cycle 1, on days 1 and 22 in cycles 2 through 4, and on days 1, 22, and 43 in all subsequent cycles or until disease progression or discontinuation of study drug for any other reason.

[figure not shown]
Note: On days 29 and 50, cemiplimab will be administered first, and ISA101b will be administered approximately 1 hour after the end of the cemiplimab infusion. Patients must be observed for 4 hours after each ISA101b administration.

The timing of doses is summarized in Figure 2. Cycle 1 will be 7 weeks long, cycles 2 through 4 will be 6 weeks long, and all subsequent cycles will be 9 weeks long.

Patients will be assessed for response at cycle 1 day 50 (week 7), then once per cycle (every 6 weeks for 3 cycles, then every 9 weeks in all subsequent cycles or until disease progression or discontinuation of study drug for any other reason; Section 8.8, Section 8.2.2, and Section 7.3, respectively). Patients with confirmed CR after a minimum of 48 weeks of treatment may elect to discontinue treatment and continue with all relevant study assessments (eg, efficacy assessments).

There will be a 90-day safety follow-up after the last dose of cemiplimab. Patients who discontinue study drug for reasons other than progression will be followed approximately every 4 months by scans until disease progression or until the patient commences another anticancer systemic therapy, whichever comes first. After progression, survival follow-up should occur approximately every 4 months.

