8.1.2. ISA101b

The study drug product ISA101b is provided in 2 vials, HPV-DP-5P containing 5 peptides and HPV-DP-7P containing 7 peptides. Bulk preparation, sterile filtration, filling, and lyophilization have been developed for each drug product. ISA101b 100 μ g/peptide will be administered by SC injections. ISA101b is not provided or prepared as an individual product. Two discrete injections, one of HPV-DP-5P and one of HPV-DP-7P, together *in vivo* constitute ISA101b.

Instructions on dose preparation are provided in the pharmacy manual.

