8.3.1.3.1. Management of ISA101b-Specific Adverse Events

ISA101b will be discontinued for any severe (\geq grade 3) ISR. Severity will be graded according to Section [10.2.5](#).

ISA101b administration should be delayed for the following:

- Any \geq grade 3 ISA101b-related AE.
- Temperature $>38^{\circ}\text{C}$ over the last 24 hours prior to administration.
- Any AE, laboratory abnormality, or intercurrent illness which, in the judgment of the investigator, warrants delaying the dose of ISA101b.

The occurrence of an ISA101b -associated systemic allergic reaction will be managed according to standard practice, including close observation, antihistamines, and fluids, as well as steroids or epinephrine if clinically indicated. ISA101b should not be administered again following resolution of a grade 4 systemic allergic reaction. Refer to the ISA101b Investigator's Brochure for details.

Local ISR at site(s) of previous administration of ISA101b of > grade 3 should be treated symptomatically and followed until resolution to grade 1 is observed.

Patients may resume treatment with the next dose of ISA101b when study drug-related AEs resolve to grade ≤ 1 or baseline value, with the following exception: patients may resume treatment in the presence of grade 2 fatigue.

If day 29 of ISA101b is missed, the second dose of ISA101b will be given on day 45 (± 3 days) and the third dose will be given on day 66 (± 3 days). If day 29 was missed due to an AE or lab abnormality, this must have resolved prior to resumption of dosing.

If day 50 of ISA101b is missed, the third dose of ISA101b will be given on day 66 (± 3 days). If day 50 was missed due to an AE or lab abnormality, this must have resolved prior to resumption of dosing.

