9. STUDY SCHEDULE OF EVENTS AND PROCEDURES

9.1. Schedule of Events

Study assessments and procedures are presented by study period and visit in [Table 2](#).

The allowable window for all visit days and assessments is ± 3 business days (excluding weekends and holidays), unless otherwise stated. All other "days" in the protocol refer to calendar days. For tumor assessments (CT or MRI), the window is ± 7 days from planned scan dates, unless otherwise stated.

Missed doses of cemiplimab or visits will not be made up. In the case of missed doses of cemiplimab, tumor assessments should still follow original schedule. If a patient is unable to undergo scans within the window due to logistical or medical reasons, tumor assessment will be obtained at the next available date.

Missed doses of ISA101b are detailed in Section [8.3.1.3.1](#).

In light of the public health emergency related to COVID-19, the continuity of clinical study conduct and oversight may require implementation of temporary or alternative mechanisms. Examples of such mechanisms may include, but are not limited to, any of the following: phone contact, virtual visits, telemedicine visits, online meetings, non-invasive remote monitoring devices, use of local clinic or laboratory locations, and home visits by skilled staff. Additionally, no waivers to deviate from protocol enrollment criteria due to COVID-19 will be granted. All temporary mechanisms utilized, and deviations from planned study procedures are to be documented as being related to COVID-19 and will remain in effect only for the duration of the public health emergency.

Table 2: Schedule of Events

Study Procedure	Screening Visit ¹	Cycle 1 ^{2,3}				Cycle 2 to 4 ^{2,3}			Cycles 5+ ^{2,3}				EOT Visit ^{4,5}	Safety Follow-up ^{4,5}	Tumor Assessment ⁵	Survival Follow-up ^{4,5}
	Day -28 to Day -1	Day 1	Day 8 ±3	Day 29 ±3	Day 50 ±3	Day 1 ±3	Day 22 ±3	Day 43 ±3	Day 1 ±3	Day 22 ±3	Day 43 ±3	Day 64 ±3	30 days after last dose ±7 days	90 days after last dose ±10 days	Every 4 months (±10 days)	Every 4 months (±10 days)
Inclusion/exclusion	X															
Informed consent ⁶	X															
Genomics substudy informed consent (optional)	X															
PBMC consent (optional)	X															
Future biomedical research consent (optional)	X															
Medical history and demographics	X															
Electrocardiogram ⁷	X												X	X		
Performance status	X												X	X		
Tumor tissue sample	X ⁶															
Treatment:																

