2.3. Study Plan

After a screening period of up to 28 days, all patients will receive the following regimen:

- ISA101b 100 µg/peptide by SC injection on Day 1, Day 29, and Day 50 (total of 3 doses).
- Cemiplimab 350 mg given by IV infusion over 30 minutes every 3 weeks (Q3W) on Days 8 and 29 in Cycle 1, on Days 1 and 22 in Cycles 2 through 4, and on Days 1, 22, and 43 in all subsequent cycles or until disease progression or discontinuation of study drug for any other reason.

Cycle 1 will be 7 weeks long, Cycles 2 through 4 will be 6 weeks long, and all subsequent cycles will be 9 weeks long.

Patients will be assessed for response at week 7, then every 6 weeks for 3 cycles, then every 9 weeks in all subsequent cycles or until disease progression or discontinuation of study drug for any other reason. Patients with confirmed CR after a minimum of 48 weeks of treatment may elect

to discontinue treatment and continue with all relevant study assessments (eg, efficacy assessments).

There will be a 90-day safety follow-up after the last dose of cemiplimab. Patients who discontinue study drug for reasons other than progression will be followed approximately every 4 months by scans until disease progression or until the patient commences another anticancer systemic therapy, whichever comes first. After progression, survival follow-up should occur approximately every 4 months.

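### SAP 5.6.2 measures ISA101b against one dose every 3 weeks, so a full course given exactly on schedule scores 90.0% relative dose intensity instead of 100%

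*SAP*

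**What the plan says.** SAP 5.6.2 defines the exposure variables for both drugs:

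- Duration in weeks is the smaller of two quantities: (last dose - first dose + 21 days)/7, and (data cut-off or death - first dose + 1)/7.
- Actual dose intensity is total dose received divided by that duration.
- "The relative dose intensity = actual dose intensity / planned dose intensity".
- Planned dose intensity is the planned dose divided by 3, per week, for ISA101b and for cemiplimab alike.

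SAP 2.3 gives ISA101b "by SC injection on Day 1, Day 29, and Day 50 (total of 3 doses"), and Protocol 6.1 gives the same schedule. Both sections attach the 3-weekly interval to cemiplimab only.

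Protocol 11.4.5.3 says: "Duration of exposure, number of doses administered, and dose intensity will be summarized". Protocol 8.2.1 says: "There will be no dose reduction for ISA101b in this study".

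**The concern.** Dividing by 3 assumes a dose every 21 days. The first ISA101b interval is 28 days, so the reference rate is higher than the rate the plan prescribes. A programmer who follows SAP 5.6.2 to the letter will report a 10% shortfall for patients who missed nothing and were never late. A reader of the study report could take it for reduced or delayed dosing. It can be neither in these patients, because ISA101b has no dose reductions and the doses in question are on time.

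The index carries some weight within the exposure section. Protocol 11.4.5.4 leaves the detailed definition of compliance to the SAP, and SAP 5.6.1 says only that administration records will be provided. Relative dose intensity is therefore the only quantity in SAP 5.6 that sets delivered against planned treatment.

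**Working it through.** The documents give no numerical relative dose intensity (RDI), so there is no stated figure to reproduce. The check applies the SAP formulas to the planned schedule.

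**Inputs.** ISA101b on days 1, 29 and 50 (SAP 2.3, Protocol 6.1); the duration rule and planned dose / 3 (SAP 5.6.2); 100 µg per peptide (SAP 2.3); 12 peptides, from "HPV-DP-5P containing 5 peptides and HPV-DP-7P containing 7 peptides" (Protocol 8.1.2).

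**Full course on schedule**

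- Duration = (50 - 1 + 21)/7 = 70/7 = 10 weeks. Three doses at the assumed rate would take 3 x 3 = 9 weeks.
- Dose per administration = 12 x 100 = 1,200 µg.
- Actual intensity = 3 x 1,200/10 = 360 µg/week.
- Planned intensity = 1,200/3 = 400 µg/week.
- RDI = 360/400 = 90.0%. The dose cancels: (3/10)/(1/3) = 0.900.

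With three doses and no truncation by death or cut-off, RDI is 100% only if the third dose falls on day 43: (43 - 1 + 21)/7 = 9 weeks. That is 7 days ahead of plan.

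**Cemiplimab as a control.** Fourteen doses every 21 days from day 8 to day 281 last (281 - 8 + 21)/7 = 42 weeks, and (14/42)/(1/3) = 100%. The mismatch is specific to ISA101b.

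**Visit windows**

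- Third dose 3 calendar days early or late: day 47 gives 67/7 = 9.571 weeks and 94.0%; day 53 gives 73/7 = 10.429 weeks and 86.3%.
- Protocol 9.1 counts the window in "business days (excluding weekends and holidays), unless otherwise stated". If it spans one weekend (±5 calendar days), day 45 gives 65/7 = 9.286 weeks and 96.9%; day 55 gives 75/7 = 10.714 weeks and 84.0%. Holidays could widen this further.

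**Other readings of SAP 5.6.2**

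- Planned dose is the three-dose total: 360/(3,600/3) = 30%.
- Duration runs over both drugs: 90% if the last study drug is on day 50; with the last cemiplimab dose on day 71, (71 - 1 + 21)/7 = 13 weeks and (3/13)/(1/3) = 69.2%. It falls further as cemiplimab continues.
- Death or cut-off before day 70 shortens the duration and raises the score: day 69 gives 69/7 = 9.857 weeks and 91.3%; day 63 gives 9 weeks and 100%; day 50 gives 50/7 = 7.143 weeks and 126%.

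**Ranking of patients, as written and with a planned rate of 3 doses per 10 weeks**

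| Doses on days | Duration (weeks) | RDI as written | RDI, planned rate 3/10 | Share of planned total |
|---|---|---|---|---|
| 1 | 21/7 = 3 | (1/3)/(1/3) = 100% | (1/3)/0.3 = 111.1% | 33% |
| 1, 29 | 49/7 = 7 | (2/7)/(1/3) = 85.7% | (2/7)/0.3 = 95.2% | 67% |
| 1, 29, 50 | 70/7 = 10 | 90.0% | 100% | 100% |
| 1, 29, 66 or 1, 45, 66 | 86/7 = 12.286 | 73.3% | 81.4% | 100% |

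The last row follows the missed-dose rule in Protocol 8.3.1.3.1 (for example, "If day 50 of ISA101b is missed, the third dose of ISA101b will be given on day 66"). Its ±3 days give 70.8% (day 69) to 75.9% (day 63) as written.

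**The case against.** The best case for leaving the text alone has four parts.

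- **The protocol asks only for dose intensity, not relative dose intensity.** That is so. The actual intensity of 360 µg/week is correct and does not use the divisor. The error lies wholly in the relative index that the SAP adds, but the SAP does say the index will be calculated.
- **A count of three doses and a rate of 90% against a 3-weekly reference can both be true.** Arithmetically they can. The fault is that the reference is labelled as planned and is not the plan. Showing three of three doses beside 90% of plan will still puzzle a reader.
- **Changing the divisor does not make the index a good one.** This stands. A patient who stops after one dose outscores one who completes the course, both as written (100% against 90.0%) and with the corrected divisor (111.1% against 100%). A rate over time on treatment does not measure completion of a fixed three-dose course, so the remedy has to go beyond the divisor.
- **Little depends on it.** Also true. Number of doses and total dosage are already planned, so full delivery can be seen directly.

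Some of the figures above are context rather than consequences of the divisor. Courses ending on day 66 are late and should score lower, and scores after early death or cut-off come from the minimum rule. None of this changes the 90.0%, and no other section of the documents corrects it.

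**Conclusion.** The concern holds, as a minor error. Followed exactly, SAP 5.6.2 gives 90.0% for a complete ISA101b course delivered on schedule, where 100% is the only sensible value.

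The figure rests on three assumptions that SAP 5.6.2 does not spell out: planned dose means the amount per administration, duration is counted separately for each drug, and neither death nor data cut-off falls before day 70. Given the third, changing either of the first two does not bring the score to 100%: it is 30% with the three-dose total, and 90% or lower with duration over both drugs.

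The consequence stops at the descriptive exposure summary. ORR, DOR, PFS, OS, the analysis sets and the subgroups do not use this index.

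**What to change.** In SAP 5.6.2:

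1. Set planned dose intensity for ISA101b to 3 x planned dose per administration / 10 weeks. Keep division by 3 for cemiplimab only.
2. State that planned dose is per administration and that duration is counted separately for each drug.
3. Add, or use in place of the relative index, total ISA101b dose received divided by the planned three-dose total, with the numbers of patients receiving 1, 2 and 3 doses. This ranks patients correctly, which the corrected rate alone does not.

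The change concerns the SAP's denominator, not the dosing schedule. It costs a revised divisor and two clarifying statements in one section, plus one row in the exposure table if the share of planned total is shown. The dose counts are already planned and no new data are needed. SAP section 1 allows revision before database lock.
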